#### 12.6.2.2 DEB-NTC

The number of subjects with events in each grade will be tabulated for the symptoms and sites shown below on the basis of the evaluation time point and treatment group. As necessary, shift tables showing Day 1 of course 1 (baseline) and certain evaluation time points will be created for each treatment group.

- > Symptoms
  - Peripheral sensory abnormalities or discomfort when touching things
  - Painless peripheral sensory abnormalities or discomfort under normal conditions
  - Painful peripheral sensory abnormalities or discomfort under normal conditions
  - · Functional disorders
- > Sites
  - Hands, feet, lips/tongue and surroundings, face, pharyngolarynx, other

# 12.6.2.3 FACT/GOG-NTX-12

Summary statistics will be calculated for FACT/GOG-NTX-12 scores and changes from Day 1 of course 1 (baseline) by evaluation time point and treatment group, and figures showing changes over time in individuals will be plotted.

#### 12.6.2.4 FACT-G

Summary statistics will be calculated for FACT-G scores and changes from Day 1 of course 1 (baseline) by evaluation time point and treatment group. Scores calculated in each of the following evaluation categories will be similarly evaluated.

➤ Evaluation categories

Physical, social/family, emotional, and functional well-being

# 12.6.2.5 NRS (pain)

For each of the sites listed below, summary statistics will be calculated for NRS scores and changes from Day 1 of course 1 (baseline) by evaluation time point and treatment group.

> Sites

Hands, feet

# 12.6.2.6 Discontinuation, Suspension, and Dose Reduction of Oxaliplatin due to CIPN

For each treatment group, Kaplan-Meier curves with the observation period and cumulative oxaliplatin dose on the horizontal axis and event incidence on the vertical axis will be plotted, with items [1] and [2] as events.

- [1] Discontinuation of oxaliplatin due to CIPN
- [2] Discontinuation, suspension, and dose reduction of oxaliplatin due to CIPN Discontinuations of oxaliplatin other than [1] and [2] is used as censored.

The numbers of subjects who undergo discontinuation, suspension, or dose reduction of oxaliplatin due to CIPN will also be tabulated.

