## 1.1.3 Oxaliplatin-induced Peripheral Neuropathy

Oxaliplatin-induced peripheral neuropathy takes the forms of acute peripheral neuropathy, which appears just after to several days after oxaliplatin administration, and chronic peripheral neuropathy, which appears later over the course of oxaliplatin treatment. Temporary numbness and abnormal sensations in the limbs and mouth, one manifestation of acute peripheral neuropathy, affect almost everyone (85% to 95%) treated with oxaliplatin. Manifestations of chronic peripheral neuropathy include persistent numbness and abnormal sensations of the limbs, fine-motor impairments such as difficulty buttoning clothing, and movement disorders such as difficulty walking. The risk of these conditions increases as the cumulative dose of oxaliplatin increases. These conditions, moreover, substantially reduce patient quality of life (QOL). The modification and discontinuation of chemotherapy caused by chronic peripheral neuropathy is particularly clinically significant .

Although the specific mechanism of the onset of oxaliplatin-induced peripheral neuropathy remains uncharacterized, chronic peripheral neuropathy is attributed to axonal degeneration resulting from nerve cell body damage. Because damaged nerves require a long time for repair, symptoms may persist for several months or years after the end of oxaliplatin treatment. Preventing the onset of oxaliplatin-induced peripheral neuropathy is therefore important.

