# 8.3.2 Changing the Dosage and Schedule of Postoperative Adjuvant Chemotherapy

This document uses the following terms in relation to changing the dosage and schedule of postoperative adjuvant chemotherapy:

Table 8.3-2 Terms related to changing the dosage and schedule of postoperative adjuvant chemotherapy

	mFOL	FOX6
	All drugs	Some drugs
Postpone	Refers to not starting administration of all drugs in the next mFOLFOX6 course on the Day 15 evaluation	-
	day.	
Suspend	-	Refers to not administering some
		drugs in a course.
Reduce (the dose)	-	Refers to reducing the dose of some drugs in a course below the
		specified dose.
Discontinue	Refers to stopping, without resumpt	ion, some or all of the mFOLFOX6
(discontinue	drugs beginning in a given course.	
treatment)		

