# 11. Completion and Discontinuation of Treatment and Observations

# 11.1 Days of Completion and Discontinuation of Individual Subjects

When a subject completes the study, promptly enter the day of completion (i.e., the day when the final tests and observations specified in the protocol are performed) in the eCRF.

When a subject is discontinued from the study, promptly enter the day of discontinuation (i.e., the day when the final tests and observations specified in the protocol are performed) and the reason for discontinuation (select the primary and other reasons from the choices in Section 11.2.1) in the eCRF.

Determine whether oxaliplatin was discontinued and, if so, promptly enter the reason for discontinuation (CIPN/adverse event/other) in the eCRF.

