# 12.6 Analysis of Efficacy

#### 12.6.1 Overall Information

This study is conducted to assess and characterize the clinical effect of ART-123 in preventing the onset of oxaliplatin-induced peripheral neuropathy and to explore appropriate efficacy endpoints. Thus, efficacy analyses will be performed primarily with descriptive statistics obtained by summarizing and graphing data from each evaluation time point.

The incidences of NCI-CTCAE Grade 1 or greater events will be evaluated with statistical tests and 95% confidence intervals as necessary in addition to descriptive statistics to allow intergroup comparison. The incidences of NCI-CTCAE Grade 1 or greater events with discontinuations and dropouts factored in will also be estimated.

The FAS will be used as the primary analysis population for evaluating efficacy. Similar analyses will be conducted as necessary with the PPS as a secondary analysis population to confirm the stability of the analysis results.

The significance level is set at 5% (two-sided), with a two-sided confidence interval and a confidence coefficient of 95%. Given the exploratory nature of the study, multiplicity will not be adjusted for.

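### The curves for oxaliplatin changes due to CIPN are labelled as incidence but censor permanent stops for other reasons, so read as incidence they overstate it

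*Protocol*

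**What the plan says.** Section 12.6.2.6 defines two events: [1] discontinuation of oxaliplatin due to CIPN, and [2] discontinuation, suspension or dose reduction due to CIPN. For each treatment group it specifies the display: "Kaplan-Meier curves with the observation period and cumulative oxaliplatin dose on the horizontal axis and event incidence on the vertical axis will be plotted". It then fixes the censoring rule: "Discontinuations of oxaliplatin other than [1] and [2] is used as censored". The same section adds a count: "The numbers of subjects who undergo discontinuation, suspension, or dose reduction of oxaliplatin due to CIPN will also be tabulated".

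Two other places bear on this. Table 8.3-2 in Section 8.3.2 defines discontinuing as a stop after which the drug is not resumed. Section 11.1 has the site record whether oxaliplatin was stopped and classify the reason as CIPN, adverse event or other.

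**The concern.** Once oxaliplatin has been stopped for good because of an adverse event or another non-CIPN reason, it can no longer be stopped, suspended or reduced because of CIPN. That stop removes the possibility of the event. It is a competing event and does not merely end observation of a risk that continues. Kaplan-Meier treats such subjects as if they would go on to have CIPN-driven changes at the same rate as those still on treatment. One minus Kaplan-Meier then estimates the risk in a hypothetical setting where nobody stops for other reasons. The axis nevertheless calls it incidence.

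This matters because, under Section 12.6.1, "efficacy analyses will be performed primarily with descriptive statistics obtained by summarizing and graphing data from each evaluation time point". No test is named for these curves, so the graph and the counts are the result. When other-cause stops precede CIPN events, the end of the curve lies above the proportion given by the tabulated counts, and the protocol does not explain why two figures for what looks like the same quantity differ. If other-cause stops differ between arms, so does the gap.

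**Working it through.** **Inputs from the protocol.** 25 subjects per group with a stated precision of ±20% (Section 12.1); 12 planned courses (Section 3.1, criterion [8]); permanent discontinuation (Table 8.3-2); censoring of non-CIPN stops (Section 12.6.2.6). The protocol gives no rate for either kind of stop, so **every rate below is an assumption**.

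**The plan's own figure.** The 95% half-width at p = 0.5 and n = 25 is 1.96 × √(0.5 × 0.5 / 25) = 0.196, and 25 is the smallest n that gives 0.20 or less. The stated ±20% reproduces and is the yardstick for the errors below.

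**Direction, from one arm of 25.** Suppose 5 subjects stop early for other reasons, 8 of the remaining 20 then have the CIPN event, and 12 complete.
- Kaplan-Meier: (19/20)(18/19)…(12/13) = 12/20 = 0.60, so the curve reads 40%.
- Actual share: 8/25 = 32%.

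The order matters. The curve exceeds the incidence only when other-cause stops come before CIPN events, and it never falls below it.

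**Size, constant hazards.** Let h be the per-course CIPN hazard and g the per-course hazard of other-cause stops.
- Cumulative incidence of the CIPN event over 12 courses = h/(h+g) × [1 − (1−h−g)^12]
- Kaplan-Meier reading = 1 − (1−h)^12

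Fix the true CIPN incidence at 30% and solve for h. For example, with 20% other-cause stops, half the subjects have some event, so h+g = 1 − 0.5^(1/12) = 0.0561. Then h = (0.30/0.50) × 0.0561 = 0.0337, and the curve reads 1 − (1−0.0337)^12 = 33.7%.

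**Size, late CIPN.** Section 1.1.3 says of the chronic neuropathy: "The risk of these conditions increases as the cumulative dose of oxaliplatin increases". As a deliberately one-sided case, the CIPN hazard is placed only in courses 7 to 12, with other-cause stops spread over all 12.

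| Other-cause stops | Plotted, constant hazards | Excess subjects per 25 | Plotted, CIPN only in courses 7–12 |
|---|---|---|---|
| 5% | 30.8% | 0.20 | 31.2% |
| 10% | 31.7% | 0.42 | 32.5% |
| 20% | 33.7% | 0.93 | 35.6% |
| 30% | 36.2% | 1.55 | 39.6% |
| 40% | 39.4% | 2.36 | 44.9% |

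The true value is 30% in every row. If all CIPN events fall in courses 1 to 6 and all other-cause stops in courses 7 to 12, the plotted value is exactly 30%.

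**Between arms.** Take two arms with the same CIPN hazard of 4.49% per course, and other-cause hazards of 1.12% and 4.09%. Cumulative incidence is 40.0% in one and 34.5% in the other, while both Kaplan-Meier curves read 42.4%. The curves show correctly that the CIPN hazards are equal. They are wrong as incidences in both arms, by 2.4 and 7.9 points.

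**The case against.** The strongest reply is that this is a matter of labelling. The section states the estimator and the censoring rule openly, so a statistician knows what is plotted, and the phrase on the axis may only mean that the curve is drawn upward; Section 12.6.2.1 words its NCI-CTCAE curves in a similar way. A Kaplan-Meier curve that censors competing events is a legitimate cause-specific display. For a question about prevention it may even be preferred, because cumulative incidence falls when more subjects stop for other reasons, as the last example shows. The tabulated counts, divided by the arm size, give the observed share directly. No endpoint is primary, the larger errors need high assumed rates, and purely late timing is least plausible for event [2], which includes suspensions and reductions.

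Most of this stands, and it limits the weight of the point. It does not remove it. The label and the censoring rule are fixed together in the protocol, and the label names a quantity that the curve does not estimate. The counts give only the final share and do not correct the curve over time. Section 12.6.2.7 allows analyses of dropout handling only where necessary, and the sentence in Section 12.6.1 on factoring in dropouts concerns Grade 1 or greater events, not this endpoint.

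**Conclusion.** The concern holds as a minor point. The direction of the error follows from the definitions and needs no assumed rate. The size depends on how many subjects stop for other reasons and when. With 5% to 10% such stops and a true incidence of 30%, the curve is about 1 to 3 points too high, at most about 0.6 of a subject per arm (2.5 points × 25) and small beside the planned ±20%. With 40% such stops it is 9 to 15 points too high. As a comparison of cause-specific CIPN hazards between arms, the curves remain fair, provided that other stops are independent of CIPN risk. The sample size is not affected.

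**What to change.** In Section 12.6.2.6, on the observation-period axis, show the incidence of [1] and of [2] as Aalen-Johansen cumulative incidence functions, with non-CIPN oxaliplatin discontinuation as the competing event, and plot the competing curve for each arm beside them. Events [1] and [2] each need their own pair, because a subject leaves the risk set for [2] at the first CIPN-driven reduction or suspension. The pair must be read together, since more non-CIPN stops alone lower the CIPN incidence. Any Kaplan-Meier curve that is kept, including the one against cumulative dose, should be labelled as cause-specific (as if no other-cause stops occurred) and not as incidence.

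The minimum change is the axis label plus the number of non-CIPN stops per arm.

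The cost is a label, a sentence and a few extra curves from a standard procedure. No new data are needed, because Section 11.1 already requires: "Determine whether oxaliplatin was discontinued and, if so, promptly enter the reason for discontinuation (CIPN/adverse event/other) in the eCRF".

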# 12.6.2.7 Other Analyses

The analyses listed below will be conducted as necessary. The details about statistical analyses will be presented in the statistical analysis plan.

- Analysis adjusted for baseline values and other covariates
- Analysis that factors in the effects of how dropouts or missing data are handled
- Subgroup analyses
- Analysis of the correlation between NCI-CTCAE grades and other efficacy endpoints
- Analysis of postoperative adjuvant chemotherapy administration status

#### 12.7 Safety Analysis

#### 12.7.1 Analysis of Adverse Events

TEAEs evaluated in the study will conform to the definition in Section 9.7.4.1. All TEAEs identified from the first day of investigational product administration to study completion (Day 43 of the last course) will be included in the tabulations. The numbers of subjects with a TEAE in each treatment group will be tabulated by adverse event name, organ class, severity (per NCI-CTCAE grading), seriousness classification, causality, and the timing of onset. Differences from the placebo group in TEAE incidences will be calculated along with two-sided 95% confidence intervals of these differences.

# 12.7.2 Analyses of Laboratory Findings

Summary statistics will be calculated according to the evaluation time point and treatment group for each laboratory parameter. Variance in each laboratory parameter will be investigated in each treatment group.

# 12.7.3 Analyses of Vital Signs

Each vital sign parameter will be analyzed as in Section 12.7.2.

# 12.7.4 Analysis of Immunogenicity (anti-drug antibodies, neutralising antibodies)

These data will be categorically tabulated by evaluation time point and treatment group.

# 12.8 Pharmacokinetic Analysis

Lists and graphs of plasma drug concentrations following investigational product administration will be created for each subject.

# 12.9 Timing of Analyses

The analyses will be performed after unblinding.

# 12.10 Reporting of Changes to the Analytical Plan

Any analyses not described in the protocol or statistical analysis plan that are additionally conducted after unblinding will be reported independently of the analyses conducted according to the protocol or statistical analysis plan.

# 13. Protocol Compliance, Deviations/Modifications, and Amendment

# 13.1 Protocol Compliance

The investigators and sponsor will conduct the study in compliance with this protocol, to which both parties have agreed. The investigators and sponsor will sign or seal and date an agreement to be decided on elsewhere.

#### 13.2 Protocol Deviations and Modifications

The investigator or subinvestigator will not deviate from or modify the protocol without prior agreement with the sponsor documented in writing and written approval based on prior review by the institutional review board. This is not applicable to protocol deviations for a medically necessary reason, such as to avoid exposing a subject to acute risk, and to clerical modifications.

If deviating from the protocol for a medically necessary reason such as to avoid exposing a subject to acute risk, the investigator will enter the reason and other pertinent information in the "Report of protocol deviation to avoid acute risk," promptly submitting this document to the study site director and sponsor. The investigator or subinvestigator will document all protocol deviations, regardless of the reason.

#### 13.3 Protocol Amendment

The sponsor may amend the protocol as necessary, for example, if obtaining information pertinent to the proper execution of the study, to address a medically unavoidable event, or to correct the protocol as instructed by the study site director based on the findings of the institutional review board.

If the protocol must be amended, the investigators and sponsor will discuss the revisions and sign or seal and date an agreement to be decided on elsewhere. The sponsor or investigators will promptly submit the amended protocol to the study site director. The approval of the institutional review board will be obtained if necessary.

# 14. Study Completion or Termination

# 14.1 Study Completion

The sponsor will promptly notify all study sites of the conclusion of registration on confirming that the number of subjects registered has reached the number of subjects targeted in the protocol and deciding that no new patients will be registered.

The investigator will inform the study site director of the completion of the study and submit a summary of the study results in writing after the treatment, examinations, observations, and tests specified in the protocol have concluded for the last patient at that study site.

# 14.2 Unblinding Following Study Completion

After study completion, the data will be unblinded according to the following procedures:

- [1] The sponsor will decide how to handle all subjects registered in the study.
- [2] The investigational product assignment manager will confirm that the investigational products are indistinguishable after study completion.
- [3] After [1] and [2], the investigational product assignment manager will retrieve the copy of key codes and emergency keys retained by the sponsor and check if they have been opened.
- [4] The investigational product assignment manager will seal the documents at data lock.
- [5] The investigational product assignment manager will conduct unblinding.

# 14.3 Termination or Suspension of the Study as a Whole or Partially

The sponsor will resolve to terminate or suspend the study as a whole or partially if determining that the study should not continue due to a serious adverse reaction or similar incident.

Subsequently, the sponsor will promptly submit a written report about study termination and the reason for termination to the investigators and subinvestigators, study site directors, and Pharmaceuticals and Medical Devices Agency (Ministry of Health, Labour and Welfare).

The investigator or subinvestigator will promptly submit written notification to the subjects, and the study site director will promptly submit written notification to the institutional review board.

#### 14.4 Termination at a Study Site

The sponsor may terminate the study at any study site where any of the situations listed below occurs. The sponsor will promptly submit written notification of the reason for termination to the study site director. The study site director will submit written notification to the investigator and the institutional review board. On receiving this notification, the investigator will follow the specified procedures for that study site.

Conditions for terminating the study at a study site

[1] When a study site commits a violation of the Japanese GCP Ministerial Ordinance, the protocol, or the study contract that interferes with the proper execution of the study, the study contract with that study site will be rendered null and void and the study will be terminated. This is not applicable when the violation is committed for a medically necessary reason such as to avoid exposing a subject to acute risk.

- [2] When a study site no longer satisfies the conditions required for properly conducting the study.
  - There are no patients that satisfy the eligibility criteria.
  - Reassignment of the investigator or a similar circumstance is found to make the proper conduct of the study infeasible.

# 15. Case Report Forms

In the study, an electronic data capture (EDC) system will be used to electronically record the subject data in the eCRFs based on the source documents. The sponsor will provide the system to the study sites. Before using the EDC system, the investigator, subinvestigator, or clinical research coordinator must undergo training and be issued an account. After an account is issued, the user will log in with his or her account and enter data.

The investigator, subinvestigator, or clinical research coordinator will enter patient registration information (e.g., inclusion/exclusion criteria eligibility) in the IWRS and transfer the data to the EDC system.

Anti-drug antibody, neutralising antibody, and pharmacokinetic measurements will not be entered in the system. Anti-drug antibody, neutralising antibody, and pharmacokinetic measurements will be electronically submitted to the sponsor by contract laboratories after unblinding.

# 15.1 Completion and Reporting of Case Report Forms

The investigator or subinvestigator or a clinical research coordinator will make entries in the eCRFs.

- [1] Clinical research coordinators are allowed to enter only information contained in the source documents.
- [2] Data are to be entered when required in the EDC system according to the sponsor-provided "Data Entry Handbook."
- [3] EDC system entry based on the source documents will be promptly completed for each subject who has given informed consent after the subject completes the follow-up period. EDC system entry will be promptly completed for any subject discontinued from the study.
- [4] The investigator will inspect all entries to confirm that no problems are present before electronically signing the eCRF. The system will be configured so that the investigators and subinvestigators cannot review FACT/GOG-NTX-12 entries, and the investigators will not electronically sign these entries.
- [5] After the sponsor locks the database, the investigator will accept electronically viewable electronic reports from the sponsor as the case report forms to be stored at the study site.

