# 9.6.3 Evaluation Methods

# 9.6.3.1 NCI-CTCAE Peripheral Motor Neuropathy, Peripheral Sensory Neuropathy (CIPN only)

The investigator or subinvestigator will evaluate neuropathy as follows:

- > Assessment time points
  - Days 1, 2, 3, 15\*1, and 29\*1 of courses 1 to 11
  - Days 1, 2, 3, and 15 of course 12
  - At Study completion
  - · At Discontinuation in the Treatment Period
  - At unscheduled CIPN evaluations
    - \*1 To be performed only in the event of postponement of the administration of all drugs for postoperative adjuvant chemotherapy

- > Information to be determined and evaluated
  - Date and time point of evaluation (before investigational product administration/after investigational product administration/not applicable)
  - Evaluate the grade on a 6-step scale (none, Grade 1 to 5) for each of the evaluation classifications (peripheral motor neuropathy, peripheral sensory neuropathy) based on the NCI-CTCAE grade classification system provided in Appendix 3
  - Assess the condition at the time of evaluation on Day 1 of course 1
  - On Days 15 and 29 of courses 1 to 11 and Day 1 of courses 2 to 12, assess the worst condition noted between the preceding evaluation (excluding any unscheduled evaluation) and the day of evaluation and the condition at the time of evaluation
  - On days of evaluation other than Day 1 and Days 15 and 29 of courses 1 through 11, assess the worst condition noted between the preceding evaluation (excluding any unscheduled evaluation) and the day of evaluation. At unscheduled CIPN evaluations, assess the worst condition noted between the preceding evaluation and the day of evaluation

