#### 9.6.3.3 FACT/GOG-NTX-12

A clinical research coordinator will have subjects complete the Japanese version of the FACT/GOG-NTX-12 (Version 4, Appendix 5) questionnaire. The clinical research coordinator will collect questionnaires from subjects and enter the date and results of evaluation in the eCRF.

- > Assessment time points
  - Days 1, 8, 15\*1, and 29\*1 of courses 1 to 11
  - Days 1, 8, and 15 of course 12
  - At Study completion
  - At Discontinuation in the Treatment Period
- > Information to be determined
  - Date and time point of evaluation (before investigational product administration/after investigational product administration/not applicable)
- > Considerations for evaluations
  - If the day of an evaluation falls on the day of an office visit, inform the subject to complete the questionnaire before the efficacy evaluation by the investigator or subinvestigator.
  - To allow the evaluation of physician-evaluated severity of peripheral neuropathy independently
    from subject evaluations, the investigator or subinvestigator and clinical research coordinator
    present during the physician evaluation of peripheral neuropathy will not review evaluations
    entered by the subjects.
  - A clinical research coordinator not present during the physician evaluation of peripheral neuropathy will collect the questionnaires from the subjects and enter them in the eCRFs without informing the investigator or subinvestigator and clinical research coordinator present during the physician evaluation of peripheral neuropathy.
    - \*1 To be performed only in the event of postponement of the administration of all drugs for postoperative adjuvant chemotherapy

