#### 9.6.3.4 FACT-G

The investigator or subinvestigator will have subjects complete the Japanese version of the FACT-G (Version 4, Appendix 6) questionnaire. The clinical research coordinator will collect questionnaires from subjects and enter the date and results of evaluation in the eCRF.

- > Assessment time points
  - Day 1 of courses 1, 5, and 9
  - Day 15 of course 12
  - At Study completion
  - At Discontinuation in the Treatment Period
- > Information to be determined
  - Date and time point of evaluation (before investigational product administration/after investigational product administration/not applicable)

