# 9.6.3.5 NRS (pain)

[figure not shown]
The investigator or subinvestigator will have subjects evaluate the severity of pain at the site subject to evaluation based on the NRS. The clinical research coordinator will collect the evaluation forms from subjects and enter the date and results of evaluation in the eCRF.

- > Assessment time points
  - Days 1, 8, 15\*1, and 29\*1 of courses 1 to 11
  - Days 1, 8, and 15 of course 12
  - · At Study completion
  - At Discontinuation in the Treatment Period

•

- > Sites subject to evaluation
  - Hands
  - Feet
- ➤ Date and time point of evaluation (before investigational product administration/after investigational product administration/not applicable)
  - \*1 To be performed only in the event of postponement of the administration of all drugs for postoperative adjuvant chemotherapy

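### Physician grading is kept independent of the subject's rating for FACT/GOG-NTX-12 only; the hand and foot pain NRS has no such rules, so its correlation with CTCAE grades may be inflated and is not comparable

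*Protocol*

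**What the plan says.** CTCAE neuropathy is graded by the physician (Section 9.6.3.1): "The investigator or subinvestigator will evaluate neuropathy as follows". DEB-NTC is graded by the same role (Section 9.6.3.2) and includes painful sensory abnormalities, with hand and foot among the sites recorded.

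Three instruments are rated by the subject (Section 9.6.1), and they are handled differently.

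- **FACT/GOG-NTX-12 (Section 9.6.3.3).** "A clinical research coordinator will have subjects complete the Japanese version of the FACT/GOG-NTX-12 (Version 4, Appendix 5) questionnaire". On office-visit days staff must "inform the subject to complete the questionnaire before the efficacy evaluation by the investigator or subinvestigator". The grading physician, and any coordinator present at the grading, do not review the subject's answers. A coordinator who was not present collects and enters them. The purpose is given: "To allow the evaluation of physician-evaluated severity of peripheral neuropathy independently" of the subject's own evaluation.
- **Pain NRS, hands and feet (Section 9.6.3.5).** "The investigator or subinvestigator will have subjects evaluate the severity of pain at the site subject to evaluation based on the NRS". A coordinator collects and enters the forms. No other rule is given.
- **FACT-G (Section 9.6.3.4).** "The investigator or subinvestigator will have subjects complete the Japanese version of the FACT-G". The collection arrangement is the same, again with no other rule.

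Section 15.1 [4] adds a restriction in the data-capture system: "The system will be configured so that the investigators and subinvestigators cannot review FACT/GOG-NTX-12 entries". It also exempts those entries from the investigator's signature. Section 12.6.2.7 lists, among analyses to be done if needed, "Analysis of the correlation between NCI-CTCAE grades and other efficacy endpoints".

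**The concern.** Section 12.6.1 gives the exploration of suitable efficacy endpoints as one purpose of the study, and Section 9.6.1 ranks no endpoint as primary. How strongly each subject-reported measure tracks the physician's grade could therefore influence which endpoint is carried into a later trial.

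That comparison is fair only if all the measures are collected with the same degree of independence. The protocol recognises the problem and solves it for one instrument. The reason it gives applies to the pain NRS as well, because the NRS rates pain at sites where the physician grades painful symptoms. If a grader sees the NRS score before grading, or the subject rates after the physician's assessment, part of the agreement could come from the collection procedure. The NRS could then look like the better companion to CTCAE for that reason alone. Independence cannot be restored once the data have been collected.

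**Working it through.** **The protocol's own figures.** It states no correlation and no degree of leakage, so there is no figure on this point to reproduce. Its one design figure is 25 per group for ±20% precision (Section 12.1). This reproduces at an incidence of 0.5: 1.96 × √(0.5 × 0.5 / 25) = 0.196. Only the total of 75 is used below.

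**The rules side by side**

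| Rule | FACT/GOG-NTX-12 (9.6.3.3) | Pain NRS (9.6.3.5) | FACT-G (9.6.3.4) |
|---|---|---|---|
| Who has the subject complete it | Coordinator | Investigator or subinvestigator | Investigator or subinvestigator |
| Completed before grading | Yes, on visit days | No rule | No rule |
| Not reviewed by the grader | Yes | No rule | No rule |
| Collector absent from grading | Yes | A coordinator, not restricted | A coordinator, not restricted |
| Hidden in data capture (15.1 [4]) | Yes | No | No |

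Section 9.6.2 does not fill the gap. It orders evaluations relative to dosing, not the subject's rating relative to the physician's grade.

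**How many ratings are exposed.** A subject who completes 12 courses without postponement gives NRS ratings on Days 1 and 8 of each course, on Day 15 of course 12 and at study completion: 12 + 12 + 1 + 1 = 26. The 12 Day 8 ratings need no office visit and no CTCAE grade falls on that day. The other 14 are taken at visits where CTCAE and DEB-NTC are also graded. FACT-G is taken only 3 + 1 + 1 = 5 times (Day 1 of courses 1, 5 and 9, Day 15 of course 12, study completion).

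**What leakage would do (illustration only).** Let G be the grade given independently and S the subject's score, both standardised, with true correlation r. Let the recorded grade be (1−w)G + wS. Both r and w are assumptions. Then

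corr = [(1−w)r + w] / √[(1−w)² + w² + 2w(1−w)r]

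- r = 0.50, w = 0.10: 0.55 / √0.91 = 0.58
- r = 0.50, w = 0.25: 0.625 / √0.8125 = 0.69
- r = 0.50, w = 0.30: 0.65 / √0.79 = 0.73
- r = 0.30, w = 0.10 to 0.30: 0.40 to 0.61
- r = 0.70, w = 0.10 to 0.30: 0.75 to 0.85
- w = 0: the correlation stays at r

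**Against sampling error.** With 75 subjects and one pair of values each, the 95% interval around r = 0.50 is tanh(atanh 0.50 ± 1.96/√72), or 0.31 to 0.65. A shift to 0.58 lies inside that interval; a shift to 0.73 lies outside it.

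**Comparability.** If FACT/GOG-NTX-12 and the NRS both truly correlated 0.50 with CTCAE, the shielded instrument would be expected to show 0.50. The unshielded one would show 0.58 to 0.73 under these weights.

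**The case against.** The strongest reply is that the selective shield follows from the choice of instruments. Section 5.2.1 names FACT/GOG-NTX-12 as the patient-reported measure of neuropathy severity, the NRS as a pain measure and FACT-G as a quality-of-life measure. On that view only the direct counterpart of the physician's grade needs shielding. This largely stands for FACT-G, which is general and rarely taken. It is weaker for the NRS, because hand and foot pain overlaps with what the physician grades in DEB-NTC.

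Several stronger readings are tempting but not supported:

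- **That the correlation is inflated.** Nothing shows that graders use the NRS answers, or that subjects rate after hearing a grade. The protocol only fails to prevent it.
- **That the grader personally administers the NRS.** The text names a role, investigator or subinvestigator, which may be filled by two people. The forms are self-rated and a coordinator collects them.
- **That investigator sign-off of the NRS and FACT-G entries contaminates the grades.** Section 15.1 [3] has entry completed after follow-up, when grades are already recorded. The data-capture restriction is therefore weak evidence, and Sections 9.6.3.3 to 9.6.3.5 carry the point.
- **That the treatment comparison is biased.** Under the double blind, leakage would not by itself favour an arm.

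It is also true that the correlation analysis is conditional, and that efficacy analysis is mainly descriptive. The no-review sentence in Section 9.6.3.3 could be read as covering all subject ratings. It stands under FACT/GOG-NTX-12 and is not repeated elsewhere, so the reading is uncertain.

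**Conclusion.** The point holds in a limited form. The independence rules cover FACT/GOG-NTX-12 only, and the gap matters most for the pain NRS at clinic visits. If the CTCAE–NRS correlation is calculated, it may be inflated by an amount that cannot be derived from the documents. The range 0.58 to 0.73 rests on an assumed true correlation of 0.50, assumed weights of 10% to 30%, and ordinal grades treated as continuous scores. It shows direction and possible scale and is not an estimate.

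What does not depend on those assumptions is that the CTCAE–NRS and CTCAE–FACT/GOG-NTX-12 correlations would be obtained under different conditions and are not directly comparable. The CTCAE–FACT/GOG-NTX-12 correlation stays protected, as do comparisons between arms. This is an inexpensive improvement to an exploratory trial, not a flaw that threatens its conclusions on treatment effect.

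**What to change.** Extend the Section 9.6.3.3 considerations to the NRS in Section 9.6.3.5. The coordinator hands out the form, the subject completes it before the physician's evaluation on visit days, a coordinator not present at the grading collects it, and the grader does not see it before grading. Apply the same to FACT-G in Section 9.6.3.4 for consistency, with lower priority. Adding both to the data-capture restriction in Section 15.1 [4] is secondary.

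The cost is a few protocol sentences. Every NRS time point is already a FACT/GOG-NTX-12 time point, and so is every FACT-G time point, so the separate coordinator is already required. The downside is that the grader does not see the NRS form before grading. The physician can still ask about pain and record adverse events as now.

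If the change is not made, state in Section 12.6.2.7 and in the report that the correlations of CTCAE grades with NRS and FACT-G are not between independent ratings and should not be ranked against the correlation with FACT/GOG-NTX-12.
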